9.3.5 Growth and Development

IGF-1 levels will be analyzed as part of the clinical laboratory testing. IGF-1 levels will be summarized on a continuous scale, including change from baseline.

Change from baseline (RCT and OLE baseline) to the end of treatment visit for IGF-1 levels will also be plotted against the Tanner Stages, weight, and height recorded at baseline.

The pubic hair growth (both sexes), genital (males only) and breast (females only) development of all adolescent patients (i.e., ≥ 7 years of age at the time of signing the informed consent form, or earlier if clinically indicated by onset of menarche or other signs of precocious puberty) will be assessed using Tanner Staging. The assessment can either be performed by examination during the study visit or the appropriate Tanner Stage can be indicated by the caregiver, with reference to the chart provided.

Patients will be examined at Visit 8, Visit 10 and Visit 14 (end of treatment). Once a patient

reaches a score of V (i.e., 5) the examination need not be performed again.

Tanner Stages will be summarized on a categorical scale by Visit. Shift table will be created to display shifts from baseline.

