6.1 Statistical Definitions and Algorithms

6.1.1 Conventions for treatment/visit naming

In all tables, listings and figures, the treatment arms will be referred to and labelled as per [Table 2](#).

Table 2 Study treatments

Endpoint	RCT Treatment	Actual Treatment	Protocol/Annex	Treatment Label (Table column/Figure legend)	Sorting order in listings, column order in tables
All	Double-Blind Treatment GWP42003-P different dosing	GWP42003-P, at different dosing	Enrolled under Protocol	Double Blind Treatment: GWP42003-P Enrolled Under Protocol	1
All	Double-Blind Treatment GWP42003-P different dosing	GWP42003-P, at different dosing	Enrolled under Annex	Double Blind Treatment: GWP42003-P Enrolled Under Annex	2
All	Double-Blind Treatment Placebo different dosing	GWP42003-P, at different dosing	Enrolled under Protocol	Double Blind Treatment: Placebo Enrolled Under Protocol	3
All	Double-Blind Treatment Placebo different dosing	GWP42003-P, at different dosing	Enrolled under Annex	Double Blind Treatment: Placebo Enrolled Under Annex	4

In all tables, listings and figures, the study visits will be referred to and labelled as per [Table 3](#).

Table 3 Study Visits

Actual Visit	Visit Label
Baseline (last record before 1 st IMP administration during lead-in trial)	RCT Baseline
Baseline (Assessment at extension Visit 1)	OLE Baseline
Visit 1: Day 1	Day 1
Visit 2: Day 8 Telephone Call	Day 8 TC
Visit 3: Day 15 Telephone Call	Day 15 TC
Visit 4: Day 29	Day 29
Visit 5: Day 57	Day 57
Visit 6: Day 85	Day 85
Visit 7: Day 141	Day 141
Visit 8: Day 197	Day 197
Visit 9: Day 281	Day 281
Visit 10: Day 365	Day 365
Visit 12: Day 547	Day 547
Visit 14: Day 729 or withdrawal	End of Treatment
Visit 15: Day 739 (end of taper)	End of Taper
Visit 16: Day 767	Follow-up

No derivation will be used for visits; data will be tabulated and listed according to the visit it was recorded under in eCRF.

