9.2 Clinical Laboratory Evaluation

9.2.1 Hematology and Biochemistry

Hematology and biochemistry safety parameters are measured at Visit 1, Visit 4, Visit 5, Visit 6, Visit 8, Visit 9, Visit 10, Visit 12 and Visit 14 (end of treatment).

Summaries will be presented for each laboratory parameter at each visit. Change from baseline (RCT and OLE baseline) and percent change from baseline to each post-baseline visit will also be presented.

If values for any of the parameters are below or above the limit of quantification of the assay (BLQ or ALQ), then they will be included in the summary tables at the BLQ or ALQ thresholds.

Where laboratory samples are repeated, the baseline value is defined as the final recorded value prior to the first dose of IMP during the lead-in trial or prior to Visit 1 in OLE trial.

Shift tables for hematology and biochemistry parameters will be produced, based upon normal ranges and GW toxicity limits (See [Appendix 3](#)), to determine the categorical shifts from each baseline (RCT and OLE) to each post-baseline visit. Values will be categorized as ‘Normal’, ‘Low’ or ‘High’ based on normal ranges and ‘Toxically Low’, ‘Toxically Normal’ or ‘Toxically High’ based on GW toxicity limits.

For eGFR, results will be assigned to the following grades:

- Normal: >60 ml/min/1.73 m²
- Grade 1: 60 ml/min/1.73 m²
- Grade 2: ≥ 30 and <60 ml/min/1.73 m²
- Grade 3: ≥ 15 and <30 ml/min/1.73 m²
- Grade 4: <15 ml/min/1.73 m²

A separate shift table will be produced for eGFR based upon the above grades to determine the categorical shifts from baseline to each post-baseline visit.

An additional table will be produced, summarizing the number of patients meeting the following criteria:

- Alanine aminotransferase (ALT) $> 1 \times \text{ULN}$ at baseline
- Aspartate aminotransferase (AST) $> 1 \times \text{ULN}$ at baseline
- AT $> 1 \times \text{ULN}$ at baseline
- Treatment-emergent ALT $> 3 \times \text{ULN}$, $> 5 \times \text{ULN}$ and $> 8 \times \text{ULN}$
- Treatment-emergent AST $> 3 \times \text{ULN}$, $> 5 \times \text{ULN}$ and $> 8 \times \text{ULN}$
- Treatment-emergent AT $> 3 \times \text{ULN}$, $> 5 \times \text{ULN}$ and $> 8 \times \text{ULN}$
- Treatment-emergent AT $> 3 \times \text{ULN}$ and either bilirubin $> 2 \times \text{ULN}$ or INR > 1.5

where AT is AST or ALT, and treatment emergent is defined as criteria not met at baseline, but

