met at any time post-baseline. The above will be summarized overall and for the following subgroups:

- Valproic acid use (as a concomitant medication) (Yes, No).
- Clobazam use (as a concomitant medication) (Yes, No).
- Valproic acid use and Clobazam use (as concomitant medications) (Yes/Yes, Yes/No, No/Yes, No/No).
(A medication will be considered concomitant if it has a start date on or after the first dose of IMP or if it was started prior to the first dose of IMP and was ongoing.)
- Patients taking 3 or more current AEDs.
- Patients taking 4 or more current AEDs.

All laboratory data will be listed; listings will include limited demographic information about the patient (age, sex, race and weight at baseline). Abnormal laboratory values will be listed separately. A further listing will be created for the laboratory reference ranges and toxicity limits. A listing of liver parameters (ALT, AST, bilirubin and INR) will be produced that includes the baseline result, result at the particular visit, change from baseline, upper limit of normal (ULN) value, ratio of result to baseline and ratio of result to ULN.

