APPENDIX 2 Toxicity Criteria for Laboratory Parameters

The toxicity criteria that will be used to identify abnormal laboratory parameters are presented in [Table 10](#) and [Table 11](#).

Table 10 Toxicity Criteria for Biochemistry Parameters

Parameter	Toxicity Decrease	Toxicity Increase
Chloride	$\leq 0.96 \times LL$	$\geq 1.04 \times UL$
Calcium	$\leq 0.89 \times LL$	$\geq 1.16 \times UL$
Sodium	$\leq 0.96 \times LL$	$\geq 1.04 \times UL$
Potassium	$\leq 0.90 \times LL$	$\geq 1.10 \times UL$
Glucose (mmol/L)	≤ 3.2	≥ 16
Phosphate	$\leq 0.79 \times LL$	
Cholesterol	$\leq 0.85 \times LL$	$\geq 1.6 \times UL$
AST		$\geq 3 \times UL$
ALT		$\geq 3 \times UL$
Lactate Dehydrogenase		$\geq 2.6 \times UL$
Alkaline phosphatase		$\geq 2 \times UL$
Gamma GT		$\geq 2.6 \times UL$
Bilirubin		$> 2 \times UL$
Albumin	$\leq 0.84 \times LL$	
Total protein	$\leq 0.84 \times LL$	$\geq 1.16 \times UL$
Urea		$\geq 2.6 \times UL$
Blood urea nitrogen		$\geq 2.6 \times UL$
Creatinine		$\geq 2.6 \times UL$
Uric acid		$\geq 1.16 \times UL$

UL = upper limit of reference range LL = lower limit of reference range

Table 11 Toxicity Criteria for Hematology Parameters

Parameter	Toxicity Decrease	Toxicity Increase
Hemoglobin (g/dL)	≤ 9.4	
Hematocrit (%)	≤ 28	
Red cell count	$\leq 0.84 \times LL$	
Mean corpuscular volume	$\leq 0.84 \times LL$	$\geq 1.11 \times UL$
Mean corpuscular hemoglobin	$\leq 0.84 \times LL$	
Mean corpuscular hemoglobin concentration	$\leq 0.84 \times LL$	
Platelets ($\times 10^9/L$)	≤ 74	
Prothrombin time		$> 1.5 \times UL$
Prothrombin international normalized ratio		> 1.5
Total white blood cell count ($\times 10^9/L$)	≤ 2.9	≥ 21
Total neutrophil count ($\times 10^9/L$)	≤ 1.36	≥ 14.7
Segmented neutrophil count ($\times 10^9/L$)	≤ 0.75	≥ 12.3
Eosinophils ($\times 10^9/L$)		≥ 1.5
Basophils ($\times 10^9/L$)		≥ 0.31

Parameter	Toxicity Decrease	Toxicity Increase
Monocytes (x10 ⁹ /L)		≥2.1
Lymphocytes (x10 ⁹ /L) for patients <18 years (auto hematology)	≤1.0	
Lymphocytes (x10 ⁹ /L) for patients <18 years (manual hematology)	≤0.2	
Lymphocytes (x10 ⁹ /L) for patients ≥18 years	≤0.2	

UL = upper limit of reference range LL = lower limit of reference range

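### The numerical IGF-1 summaries are not standardised or split by age or sex, so in this single-arm paediatric trial the mean change mixes maturation with any drug effect; the planned plots and shift tables address this only in part

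*SAP*

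**What the plan says.** Protocol V2 section 13.6.2 and SAP 2.2.2 place serum IGF-1 with height, weight and Tanner stage under change in growth and development, within the primary safety endpoint. IGF-1 is sampled at Visits 1, 8, 10 and 14 (SAP Table 1, footnote h).

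The planned outputs that touch IGF-1 are:

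- **Level and change.** SAP 9.3.5: "IGF-1 levels will be summarized on a continuous scale, including change from baseline".
- **Percent change.** IGF-1 is in the biochemistry column of Protocol Table 9.2.9-1, so SAP 9.2.1 applies: "percent change from baseline to each post-baseline visit will also be presented".
- **Plots.** SAP 9.3.5 has the change to end of treatment, from both the RCT and the OLE baseline, "plotted against the Tanner Stages, weight, and height recorded at baseline".
- **Shift tables.** SAP 9.2.1: "Shift tables for hematology and biochemistry parameters will be produced, based upon normal ranges and GW toxicity limits".
- **Listings.** SAP 9.2.1: "All laboratory data will be listed; listings will include limited demographic information about the patient (age, sex, race and weight at baseline)".

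SAP Table 2 gives four table columns, formed by prior RCT arm and by enrolment under protocol or annex. The age groups 2-5, 6-12 and 13-19 appear in SAP 7.3 for demographics. The laboratory subgroups in SAP 9.2.1 (valproate, clobazam, number of AEDs) belong to the liver criteria.

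**The concern.** The population runs from toddlers to late adolescents of both sexes, maintenance is planned for up to 104 weeks, and there is no untreated group. Whatever IGF-1 would have done with age goes into the same mean as any effect of the drug. That mean then depends on the age mix and on how long each patient was followed. A drug-related fall could be partly hidden by a rise with age, or an ordinary change with age could be read as a drug effect.

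The SAP's choice of Tanner stage, weight and height as plotting axes suggests that maturity was thought relevant to IGF-1. The tables do not carry that through.

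**Working it through.** The plan has no figure to reproduce: no sample size calculation, no IGF-1 SD and no expected change. The main check is to read the planned outputs against the question of how far IGF-1 moved beyond what age alone would produce.

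**What each output can show**

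1. *Level, change, percent change.* These give size, by visit and from both baselines, but with no age or sex split and no standardised score.
2. *Plots.* These give size against maturity and body size, so they do help. They use maturity at baseline only, cover end of treatment but not Days 197 or 365, and carry no expected-change reference. Tanner staging is routine only from age 7. For the OLE baseline, Tanner stage and height are not scheduled at Visit 1, except for annex patients enrolling after RCT Visit 11 (annex version 2, section 3.2.1).
3. *Shift tables.* These show crossings of the normal range, not size. The documents do not say whether the IGF-1 range is age- and sex-specific. The SAP appendix that begins "The toxicity criteria that will be used to identify abnormal laboratory parameters are presented in" has no IGF-1 row in its biochemistry table (Table 10).
4. *Table columns.* Both prior RCT arms take GWP42003-P in the extension, so neither is an untreated reference.
5. *Listings.* Age and sex stand beside each value, patient by patient, without a summary.

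**Elapsed time**

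SAP Table 3 labels "Visit 14: Day 729 or withdrawal" as end of treatment, and SAP 6.1.1 adds "No derivation will be used for visits; data will be tabulated and listed according to the visit it was recorded under in eCRF". That row can therefore hold very different durations. Visit 1 blood is required only when entry is more than 28 days after RCT Visit 9 (SAP Table 1, footnote f), while same-day entry is recommended. Some patients may therefore have only the longer change from RCT baseline; how many cannot be told from the documents.

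**Illustration only**

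The documents give no IGF-1 drift, suppression, age mix or RCT length, so all of these are assumed:

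- L = weeks from RCT baseline to OLE Day 1, taken as 24;
- s = true suppression, taken as 0.10;
- p = share of older patients, 0 to 1;
- drift +10% per year in younger and -5% per year in older patients.

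T = (day - 1 + 7L)/365.25. Day 197: (196 + 168)/365.25 = 1.00 years. Day 365: (364 + 168)/365.25 = 1.46 years.

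Pooled % change = 100 × {p[(1 - s)(0.95)^T - 1] + (1 - p)[(1 - s)(1.10)^T - 1]}.

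At Day 197, the younger term is 0.90 × 1.0996 - 1 = -1.0% and the older term is 0.90 × 0.9502 - 1 = -14.5%.

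| p | 0 | 0.25 | 0.50 | 0.75 | 1 |
|---|---|---|---|---|---|
| Day 197, s = 0.10 | -1.0 | -4.4 | -7.8 | -11.1 | -14.5 |
| Day 365, s = 0.10 | +3.4 | -1.6 | -6.5 | -11.5 | -16.5 |
| Day 197, s = 0 | +10.0 | +6.2 | +2.5 | -1.2 | -5.0 |
| Day 365, s = 0 | +14.9 | +9.4 | +3.8 | -1.7 | -7.2 |

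Sensitivity with s = 0.10:

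- L = 12 gives -3.2 to -13.5% at Day 197; L = 36 gives +1.2 to -15.5%.
- Drift of +2% and -2% per year with L = 24 gives -8.2 to -11.8% at Day 197 and -7.4 to -12.6% at Day 365.

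The assumed drift largely determines the size of the spread.

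**The case against.** A reader might infer that IGF-1 change is planned only as raw pooled numbers, with nothing that relates it to maturity. The documents do not support that. The plots in SAP 9.3.5 set the size of the change against baseline Tanner stage, weight and height; the shift tables cover biochemistry; and the columns separate prior arm and enrolment route. Pooling is a fair description for age and sex only.

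Several further points carry weight:

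- **The illustration is not evidence of size.** Mild drift makes the mixing small, and a balanced age mix partly cancels it (-7.8% against a true -10% at Day 197 under the larger drifts). SAP section 1 says the extension is stopped prematurely, so long follow-up may be uncommon.
- **Part of the remedy may already exist.** The laboratory's IGF-1 range may be age- and sex-specific, and the table shells are a separate document that was not available.
- **A general reference may fit Rett patients imperfectly.** Pubertal stage may be a useful axis in this population, and the SAP already uses it.
- **Little is lost.** The analysis is descriptive, all values are listed with age and sex, and the SAP permits labelled post-hoc analyses. Height, weight and Tanner outputs also inform the growth question.

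These points limit the size and seriousness of the concern. They do not supply an age- and sex-standardised numerical summary, and the possibility of a post-hoc analysis does not improve the planned one.

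**Conclusion.** The concern holds in a limited form. The level, change and percent-change summaries of IGF-1 are neither standardised nor split by age or sex, and there is no concurrent control, so the mean change cannot by itself distinguish maturation from a drug effect. The plots and shift tables reduce the problem without removing it.

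The size of the mixing cannot be estimated from the documents. The figures above rest wholly on assumed drift, suppression, age mix and lead-in length, and should not be read as showing that a drug effect would be masked or manufactured here. Nor does the point undermine the primary safety endpoint as a whole: IGF-1 is one of four growth measures within one of eight listed safety components, and no data are lost. What suffers is how readable the IGF-1 result is. This is a worthwhile, inexpensive improvement. The finding is made on the SAP text without sight of the shells.

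**What to change.** In SAP 9.3.5, keep the raw summaries and the baseline plots, and add a by-visit summary of IGF-1 level and change as an age- and sex-specific SD score, or as position within the central laboratory's age- and sex-specific range. Use age at each sample. Present it from the RCT baseline and, where a Visit 1 sample exists, from the OLE baseline with its n.

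If no such reference data are available, present IGF-1 by the age groups already defined in SAP 7.3 (2-5, 6-12, 13-19), with a note that this reduces maturation but does not remove it.

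The cost is SAP wording and a few extra tables from data already collected, some with small cells. The score depends on what the laboratory can supply, since Protocol 9.2.9 promises normal ranges without saying whether they are age-specific. A general reference may not fit Rett patients exactly, and a single-arm trial still could not attribute the remaining change fully to the drug.

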9 TRIAL PROCEDURES

A list of the required trial procedures is provided in the subsections that follow; refer also to the schedule of assessments ([Appendix 1](#)). Assessments or tests that are not done and examinations that are not conducted must be reported as such on the eCRF.

The location of the source data for the following procedures will be documented, per center, in a signed source data verification plan; for further details, see [Section 16.2](#).

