9.2.13 Tanner Staging

The pubic hair growth and breast development of all adolescent patients (i.e., ≥ 7 years of age⁷¹ at the time of signing the ICF or earlier, if clinically indicated by the onset of menarche or other signs of precocious puberty) will be assessed using Tanner Staging.⁷² The assessment can either be performed by examination during the study visit or the appropriate Tanner Stage can be indicated by the caregiver, with reference to the chart provided.'

Once a patient reaches a score of V (i.e., 5) the assessment need not be performed again.

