13.6.5 Handling of Missing Data

There will be no imputation of missing data, and all observed data will be summarized.

Study Code: GWND19002
EudraCT Number: 2019-001605-24
Clinical Protocol V2 18Dec19

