6.1.6.1 Handling of Missing Data for Efficacy Endpoint (Primary, Secondary and Exploratory)

If a questionnaire has subscales then the missing items in a subscale can be imputed as the mean of the non-missing items in that subscale, provided that at least half of the items in the subscale were answered. If more than half the items in the subscale are missing then the missing items will be imputed as LOCF.

If a questionnaire does not have subscales (eg MBA-9, CSHQ single item scale) the missing items will be imputed using LOCF.

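### Tanner stage V patients need not be restaged and no rule counts them as stage V later, so the by-visit table understates stage V and the shift table can be distorted either way

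*SAP*

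**What the plan says.** Growth and development, including Tanner stage, is a component of the primary safety endpoint (Protocol 4.1.1; SAP 2.2.2). On timing, SAP 9.3.5 states: "Patients will be examined at Visit 8, Visit 10 and Visit 14 (end of treatment)". These are Days 197, 365 and 729, and Visit 14 also serves as the withdrawal visit.

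The protocol then relaxes the schedule: "Once a patient reaches a score of V (i.e., 5) the assessment need not be performed again" (Protocol 9.2.13). SAP 9.3.5 repeats this for a patient who "reaches a score of V (i.e., 5) the examination need not be performed again". The planned outputs are: "Tanner Stages will be summarized on a categorical scale by Visit. Shift table will be created to display shifts from baseline".

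Four other provisions determine what those outputs will contain:

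- Protocol 9, on omitted assessments: "Assessments or tests that are not done and examinations that are not conducted must be reported as such on the eCRF".
- Protocol 13.6.5, on missing data: "There will be no imputation of missing data, and all observed data will be summarized".
- SAP 6.1.6.1, under a heading limited to efficacy endpoints: "If a questionnaire does not have subscales (eg MBA-9, CSHQ single item scale) the missing items will be imputed using LOCF".
- SAP 6.1.1, on visits: "No derivation will be used for visits; data will be tabulated and listed according to the visit it was recorded under in eCRF".

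SAP 4.1 sets the default percentage denominator as everyone in the study population, and counts as missing everyone in that total without a value.

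**The concern.** The plan permits a value to be absent because the outcome has reached its top category, then tabulates the remaining values as if absence carried no information. The patients most likely to drop out of a later Tanner column are the most mature ones.

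This is foreseeable here. Lead-in entry covers ages 2 to 18 (SAP 3.3), staging applies from age 7 or earlier if indicated, and the SAP's oldest age band is 13 to 19 (SAP 7.3). Some patients at stage V, including some already there in the RCT, should be expected.

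What is at stake is whether the pubertal-development tables can be read. Under the default conventions a single missing count would combine three groups: patients too young to be staged, mature patients not restaged, and patients whose assessment was simply missed. A reader could not recover the stage V share from the table.

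**Working it through.** The plan states no figure for this point, so there is none to reproduce. The check follows one patient through the rules, then does the bookkeeping on assumed counts.

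**Tracing the rules.** Take a patient first recorded as V at Visit 8.

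1. At Visit 8 she is staged and appears as V, in the by-visit table and in any shift to that visit.
2. At Visit 10 she need not be restaged. If she is not, the eCRF records the assessment as not done and no stage exists for that visit.
3. Nothing restores the value. Imputation is barred by the protocol. The carry-forward rule covers efficacy questionnaire items, and Tanner stage is a safety endpoint. The last-visit definition in SAP 6.1.3 is not linked to the Tanner outputs.
4. She is counted as missing at Visit 10, and again at Visit 14 if not restaged.

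If the stop rule is applied to a V reached in the RCT, a patient already at V at RCT baseline may have a baseline row and no OLE stage at all.

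**Bookkeeping.** Assume N = 100 Tanner-eligible patients who all attend the tabulated visit. The counts below are illustrative; the documents give none.

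- a = at V at RCT baseline, not restaged
- b = reached V after baseline and before the tabulated visit, not restaged
- c = progressed from baseline and staged at the visit
- v = recorded as V at the visit

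*By-visit stage V share.* True share = (v + a + b)/N. Shown on a fixed denominator = v/N. Shortfall = (a + b)/N, that is, every unrestaged stage V patient. If percentages use staged patients only, the table shows v/(N − a − b). This cannot exceed the true share, because v cannot exceed N − a − b.

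*Shift table, share who progressed.* True = (b + c)/N. Fixed denominator = c/N. Staged-only = c/(N − a − b).

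| a | b | c | Stage V shortfall, by-visit, (a + b)/N | True progressed | Fixed denominator | Staged-only |
|---|---|---|---|---|---|---|
| 0 | 10 | 20 | 10 points | 30.0% | 20.0% | 20/90 = 22.2% |
| 10 | 10 | 20 | 20 points | 30.0% | 20.0% | 20/80 = 25.0% |
| 30 | 5 | 20 | 35 points | 25.0% | 20.0% | 20/65 = 30.8% |
| 30 | 0 | 20 | 30 points | 20.0% | 20.0% | 20/70 = 28.6% |

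The by-visit stage V share is too low in every row. On the fixed denominator the shift table falls short by b/N, which is zero when b = 0. On the staged-only denominator it is too low in the first two rows and too high in the last two. Patients at V at baseline cannot progress, so dropping them removes non-progressors.

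The SAP's default denominator would also include patients not eligible for staging. That shrinks the true and shown fixed-denominator percentages in the same proportion and does not change the direction.

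**The case against.** The strongest reply has five parts.

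- **Restaging is optional.** The schedule still lists Tanner staging at Visits 8, 10 and 14 where appropriate. If sites restage everyone, nothing is lost. This stands: the size cannot be known from the documents.
- **The supporting rules are softer than they look.** The visit rule in SAP 6.1.1 sits under naming conventions and mainly governs visit assignment. The SAP already departs from the protocol's no-imputation rule for questionnaire items and adverse event dates. This is fair, but neither point supplies a rule for Tanner stage.
- **The data are recoverable.** All collected data are listed, and SAP 6.1.8 lets further derivations for primary endpoints be described in the study report without amending the SAP. That helps a later analyst but does not correct the planned tables.
- **The trial is single-arm and descriptive.** Even complete Tanner tables could not isolate a drug effect. This limits the consequence; it does not make the table accurate.
- **Early stopping reduces exposure to the problem.** SAP section 1 says the extension is stopped prematurely. A patient whose only OLE Tanner visit is the withdrawal visit cannot lose a stage V reached in the OLE, though one recorded in the RCT could still be lost.

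A reader might go further and infer that patients stop being staged at V, that moves from IV to V vanish, or that the End of Treatment column of the shift table loses them. The documents do not support these readings. Staging is waived, not prohibited; a move to V is captured at the visit where it is first recorded; and SAP 9.3.5 names no post-baseline visit for the shift table, whose shell is in a separate document.

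**Conclusion.** The gap is real. As written, a stage V patient who is not restaged is missing at later Tanner visits because the outcome reached its maximum, and the by-visit stage V share is understated by every such patient on the default denominator. This assumes that the stop rule is used, that the patient attends the later visit, and that stage V does not revert.

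It is tempting to conclude that the plan understates pubertal progression overall. That does not follow. In the shift table the error can be downward, absent or upward, depending on the denominator and on how many patients were at V at baseline. The percentages above illustrate direction only and do not estimate what happened in this trial.

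The matter is worth correcting because the table reports a component of the primary safety endpoint and the correction uses data already collected. No hypothesis test is affected.

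**What to change.** Add to SAP 9.3.5:

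- A patient with a recorded overall Tanner score of V at any RCT or OLE assessment is counted as stage V at every later scheduled Tanner visit attended, in both the by-visit and shift tables, unless restaged with a different recorded value. State this as an exception to the no-imputation rule.
- Percentages use Tanner-eligible patients as the denominator, with not done shown as a separate row.
- The shift table's post-baseline visit or visits are named.

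The reference to an overall score matters because SAP 9.3.5 covers pubic hair together with breast or genital development, and V in one component should not trigger the rule.

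The cost is a few SAP sentences and a small amount of programming. There is one small downside. Stage may be indicated by a caregiver from a chart, so a V recorded in error would be carried forward. The exception for a different restaged value limits this, and the listings would still show where V was actually recorded.
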